4.5.2.4. Interim Visits as part of Standard of Care

At any time between study visits, clinical data and leftover specimen material collected as part of SoC visits could also be included in the study if shared by the attending clinician. These interim visits are independent of the study and may or may not occur depending on SoC procedures.

4.5.3. End of Study Criteria

1. Completion of de-identified sample analysis
2. Hospital discharge after Visit 2
3. Completion of Visit 2 if discharged from hospital prior to Visit 2
4. Participant or parent/LAR withdraws study participation
5. Participant is lost to follow-up or moves away from the study area
6. Participant dies
7. Participant was inadvertently enrolled
8. Investigator determines that further participation would be detrimental to the health or well-being of the participant
9. The study is stopped for other administrative reasons

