Visit schedule for prospective study arm of ongoing patients providing informed consent	
Study Visit 1: Enrollment and Baseline Visit (Day 0)
 
 1. Demographics including, but not limited to: sex, age, residence, occupation. 2. Medical history including, but not limited to: travel history, insect and animal exposure, vaccination history, medication use prior to enrollment. 3. Clinical data including, but not limited to: current signs and symptoms, height and weight, vital signs, comorbidities, treatment, clinical outcome at this visit, available SoC laboratory or imaging results. 4. Specimen collection (when possible): whole blood (5-15 mL) and clinically indicated non-invasive specimens such as sputum, urine, stool, nasopharyngeal swab, etc. Specimens collected under SoC can also be included in the study if leftover material is shared. 5. Laboratory testing: routine hematology, blood chemistry, liver function tests, and renal function tests. 
Study Visit 2: Follow-Up Visit (between Day 7-14)
 
 1. Clinical data including, but not limited to: current signs and symptoms, height (if previously not done) and weight, vital signs, comorbidities, treatment, clinical outcome at this visit, available SoC laboratory or imaging results. 2. Specimen collection (when possible): whole blood (5-15 mL) and clinically indicated non-invasive specimens such as sputum,

	
urine, stool, nasopharyngeal swab, etc. Specimens collected under SoC can also be included in the study if leftover material is shared.
 
3. Clinical outcome data at hospital discharge or death (when applicable).

	
Study Visits After Visit 2, if Needed
 
1. Clinical data including, but not limited to: current signs and symptoms, height (if previously not done) and weight, vital signs, comorbidities, treatment, clinical outcome at this visit, available SoC laboratory or imaging results.
 
2. Specimen collection (when possible): whole blood (5-15 mL) and clinically indicated non-invasive specimens such as sputum, urine, stool, nasopharyngeal swab, etc. Specimens collected under SoC can also be included in the study if leftover material is shared.
 
3. Clinical outcome data at hospital discharge or death (when applicable).

Interim Visits as part of Standard of Care

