0), and clinical data and biological specimens will be collected one time at study visit 2 (follow-up visit between Day 7-14), as well as at any necessary study visits after Visit 2. **Blood samples (5-15 mL) and clinically indicated non-invasive samples such as sputum, urine, stool, nasopharyngeal swab, etc., will be collected from all participants at each study visit, when possible. If there is a risk to the participant's safety, such as a bleeding disorder, or if the maximum allowable limits for sample collection have been reached by SoC procedures or other studies, then samples will not be collected.** Specimens collected under SoC visit(s) could be included in the study if leftover specimen material is shared by the attending clinician. **Clinical data collected as part of SoC visit(s) could also be included in the study if shared by the attending clinician. If SoC visits and procedures occur between study visits, the data and leftover specimens shared with the study from these visits and procedures will be considered as part of interim visits. These interim visit(s) are independent of the study and may or may not occur depending on SoC.** Whenever possible, any specimen material remaining after study testing is complete will be cryopreserved and stored indefinitely for future research such as, but not limited to, developing and validating diagnostic tests, determining the evolution of pathogens, and determining host disease susceptibility.

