4.5.2. Visit Schedule and Procedures

Clinical and laboratory evaluations will be performed for each participant after they have provided a documented informed consent or assent with parental/LAR consent. If the study team is unable to obtain a documented informed consent for reasons other than the patient declining participation in the study, the patient can still be enrolled in the study in a de-identified manner. Any data collected by health authorities as part of SoC will be scrubbed of personally identifiable information (PII), such as date of birth, residence, and other variables that may vary depending on the circumstances and/or scale of the individual outbreak. Prior to receiving any patient data, the core study team will consult with the relevant health authorities to determine what metadata will be included with the de-identified samples.

See Appendices 1 and 2 for general specimen types and collection guidelines. A general study timeline for ongoing patients with difficult infections of unidentified etiology is shown in Figure 4.

[figure not shown]

Figure 4 Study timeline for ongoing patients with difficult infections of unidentified etiology.

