4.5.2.2. Study Visit 2: Follow-Up Visit (Day 7-14)

The following procedures will be completed at the follow-up visit (one time between Day 7-14):

1. Clinical data including, but not limited to: current signs and symptoms, height (if previously not done) and weight, vital signs, comorbidities, treatment, clinical outcome at this visit, available SoC laboratory or imaging results.
2. Specimen collection (**when possible**): whole blood (5-15 mL) and clinically indicated non-invasive specimens such as sputum, urine, stool, nasopharyngeal swab, etc. Specimens collected under SoC can also be included in the study if leftover material is shared.
3. Clinical outcome data at hospital discharge or death (when applicable).

4.5.2.3. Study Visits After Visit 2

Study visits **after Visit 2** may be necessary depending on the complexity of the ongoing case. Such cases could include those where convalescent specimens are needed to definitively identify an etiology, or those where long-term sequelae of interest are observed or anticipated. **If study visits after Visit 2 are needed**, then the following procedures will be completed:

1. Clinical data including, but not limited to: current signs and symptoms, height (if previously not done) and weight, vital signs, comorbidities, treatment, clinical outcome at this visit, available SoC laboratory or imaging results.
2. Specimen collection (**when possible**): whole blood (5-15 mL) and clinically indicated non-invasive specimens such as sputum, urine, stool, nasopharyngeal swab, etc. Specimens collected under SoC can also be included in the study if leftover material is shared.
3. Clinical outcome data at hospital discharge or death (**when applicable**).

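### The end-of-study criteria in Section 4.5.3 close participation at Visit 2 or at discharge, with no exception for the later visits that Section 4.5.2.3 allows

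*Combined protocol and SAP*

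**What the plan says.** **Visits.** Section 4.5.2.2 has the follow-up procedures "completed at the follow-up visit (one time between Day 7-14"). Section 4.5.2.3 then allows further visits for complex cases. It gives two examples: cases "where convalescent specimens are needed to definitively identify an etiology", and cases in which "long-term sequelae of interest are observed or anticipated". The Protocol Summary has a block headed "Study Visits After Visit 2, if Needed". Section 4.1 includes collection "as well as at any necessary study visits after Visit 2". The COVID-19 annex allows one more visit after Visit 2 and sets no time frame for it. None of these places limits the later visits to inpatients.

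**End of participation.** Section 4.5.3 has nine criteria. Item 2 is "Hospital discharge after Visit 2" and item 3 is "Completion of Visit 2 if discharged from hospital prior to Visit 2". No item refers to visits after Visit 2.

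**Specimen timing.** Section 4.5.2 tells the reader: "See Appendices 1 and 2 for general specimen types and collection guidelines". Both appendices are titled as general guidance, and Appendix 2 is written for outbreaks with an unknown pathogen. They define the specimens in three ways:

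- Appendix 1 (table): acute serum is Day 0 to 14 and convalescent serum is after day 14. The origin of the day count is not stated.
- Appendix 2, general principle 3: acute is at most 7 days from onset; convalescent is more than 14 days into symptoms.
- Appendix 2, section C.1 (serum and plasma): acute is within one week of onset; convalescent is after day 14 counted from the acute specimen.

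**The concern.** Identifying the causative agent is the primary objective, and Section 4.5.2.3 itself says that a convalescent specimen may be needed for a definitive identification. Appendix 2 adds that for most respiratory pathogens a definitive diagnosis requires both sera. If the end-of-study criteria are applied as written, a discharged participant has left the study before such a visit can take place. Follow-up of long-term sequelae after discharge is cut off in the same way.

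Sites could also diverge. One could close a participant at Visit 2 and another bring a similar participant back, each citing the protocol, while Section 10 has monitors check procedures against that same protocol.

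The differing specimen definitions add a smaller problem: one Visit 2 serum can be called convalescent under one rule and not under another.

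**Working it through.** The plan gives no figure to reproduce here. The check compares the rules and counts days.

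**1. Stop rule against later visits**

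| Participant | Section 4.5.3, read literally | Visits under 4.5.2.3 |
|---|---|---|
| Discharged before Visit 2 | Item 3: ends at Visit 2 (Day 7 to 14) | None possible |
| In hospital at Visit 2, discharged later | Item 2: ends at discharge | Only until discharge |
| Still in hospital | Neither item triggered | Possible |
| De-identified case | Item 1: ends when sample analysis is complete | Not affected by items 2 and 3 |

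Later visits are provided for in four places (Protocol Summary, 4.1, 4.5.2.3, annex). None of the nine criteria excepts them.

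**2. Can Visit 2 supply the convalescent serum?**

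Inputs: Visit 2 on study day d = 7 to 14, which is 14 − 7 + 1 = 8 days (4.5.2.2). The acute specimen is drawn k days before Day 0, where k = 0 means it is drawn at Visit 1. Symptom onset is x days before Day 0. The documents give neither k nor x, so both are varied.

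- *Appendix 2, C.1 (from the acute specimen):* qualifies if d + k > 14. With k = 0 this needs d > 14, so 0 of 8 days qualify. In general k of 8 qualify for k = 0 to 8; for example, k = 3 gives d = 12, 13 and 14, or 3 of 8. An earlier acute specimen is possible if leftover standard-of-care material is shared.
- *Appendix 2, principle 3 (from symptoms):* qualifies if d + x > 14. This gives 0 of 8 at x = 0, 3 of 8 at x = 3, 7 of 8 at x = 7, and 8 of 8 from x = 8 on.
- *Appendix 1:* if day means study day, all 8 Visit 2 days fall in the acute column. If it means days from onset, the convalescent count equals that of principle 3.

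So under C.1 with a Day 0 acute draw, the earliest convalescent day is Day 15. The latest possible Visit 2 is Day 14, the last day on which item 3 leaves an already discharged participant in the study.

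**3. How the definitions relate**

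If the acute specimen is not drawn before onset, then k ≤ x, and d + k > 14 implies d + x > 14. A serum that meets C.1 therefore also meets principle 3: the rules nest. They label min(x, 8) − min(k, 8) of the 8 Visit 2 days differently. With x = 3 and k = 0 that is 3 − 0 = 3 days.

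For acute serum, principle 3 and C.1 agree on about one week from onset. Appendix 1, read from onset, also counts days 8 to 14 (14 − 8 + 1 = 7 days) as acute.

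**4. Where serology matters**

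Appendix 5 lists seroconversion or a titre rise as a confirmation route for about eleven targets: dengue, Salmonella, *R. typhi*, *O. tsutsugamushi*, Leptospira, chikungunya, Seoul/hantavirus, rubella, influenza, RSV and measles. Some rows are misaligned in the text available, so the count is approximate. Ten also list a molecular method; rubella does not.

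**The case against.** **Items 2 and 3 may be the default end, with 4.5.2.3 as the specific exception.** Section 7 asks for visit-schedule decisions to be documented, and Section 4.1 allows case-specific annexes, so later visits are evidently managed case by case. This is probably the intent. But neither provision amends Section 4.5.3, and no text says which section prevails.

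**Section 4.5.2.3 may mean inpatient visits only.** It does not say so. Its discharge-or-death item applies only where relevant, and follow-up of long-term sequelae fits poorly with a rule that ends at discharge.

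**The practical effect may be small.** Much of this stands. Specimens are collected only when possible. Most serology targets also have a molecular method. Appendix 5 accepts some single-specimen evidence: supported IgM for dengue, IgM in an acute sample for Salmonella, and a high titre in one acute sample for Leptospira. It sets no minimum day, so a rise already present at Visit 2 can count.

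**Stronger readings that the documents do not support.**

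- A reader might infer that the convalescent rules cannot all be met. They nest, so with a Day 0 acute draw any serum after Day 14 meets all of them.
- A reader might blame the differing definitions for the lack of a guaranteed convalescent serum. That follows from the C.1 rule and the Visit 2 window alone.
- A reader might take the further testing in Section 5 to mean a new blood draw after discharge. It concerns specimens already held.
- A reader might think the annex leaves its specimen rules open. It refers to the main protocol for data and specimens, and so inherits the inconsistency.

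**Conclusion.** The conflict stands and should be fixed. Read literally, items 2 and 3 of Section 4.5.3 close the visits that four other places provide for, in discharged participants seen by the study team. With a Day 0 acute specimen, 0 of 8 Visit 2 days meet the Appendix 2 serum timing, so a convalescent serum on that definition needs one of those visits. This rests on a literal reading of Section 4.5.3 and on an acute specimen drawn at Visit 1; an earlier acute specimen changes the count to k of 8. Figure 4, the study timeline, was not visible in the text available and should be checked.

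A reader might infer that a known share of diagnoses would be lost. The documents give no onset times, discharge times or numbers of later visits, so that share cannot be computed.

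The differences between Appendices 1 and 2 are a secondary point: an inconsistency of labelling in general guidance, which changes no confirmation threshold in Appendix 5.

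**What to change.** 1. Reconcile Section 4.5.3, items 2 and 3, with Section 4.5.2.3, so that the end-of-study criteria do not close participation while a visit under 4.5.2.3 is outstanding.
2. Reconcile Appendix 1 with the two timing statements in Appendix 2 (general principle 3 and section C.1) on what counts as an acute and a convalescent specimen, and state the origin of the day count. The annex would inherit the result through its reference to the main protocol. Which timing to adopt is for the sponsor to decide.

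The cost is an amendment to protocol and appendix wording, plus some return visits of a kind that Section 4.5.2.3 already allows.

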4.6. Retrospective Study

4.6.1. Eligibility Criteria

4.6.1.1. Inclusion criteria

1. Samples from an adult or child of any age who experienced a presumed infectious disease of unidentified etiology
2. Current episode of illness has ended

4.6.1.2. Exclusion criteria

1. Positive for Dengue virus infection, if results are available
2. Positive for *Salmonella* Typhi infection, if results are available

4.6.2. End of study criteria

1. Completion of sample analysis
2. Depletion of available samples

4.7. Defining Difficult Cases of Unidentified Etiology

While this study aims to assist clinicians at the hospitals when they have difficult infectious disease of unidentified etiology, it should be clear that this is a research study and not simply an advanced diagnostic laboratory. Sites may or may not receive etiology results before a patient is discharged

Several etiologies can only be confirmed using fresh specimens and culture, for example, blood culture for sepsis, and urine culture for urinary tract infection. Therefore, it is expected that clinicians have conducted the search of the pathogens based on the available facilities at their hospitals and/or diagnostic laboratories in their region. INA-RESPOND laboratory does not have the capacity to test for pathogens that only can be identified by these cultures.

Hospital should also take advantage of any other clinical testing they have on-site, such as microscopy or RDTs, so that the patient receives the fullest possible benefit. For screening dengue, sites should test for NS1 and IgM/IgG antibody using at least rapid diagnostic test and for screening typhoid fever using blood culture or tubex (≥ 6). Although clinicians may not think of these diseases as the causes of the diseases, ORCHID requires these tests to ensure that our study is not flooded with dengue and typhoid

fever as it will reduce the essence of our aim. Furthermore, based on the AFIRE study, approximately 20% of unsuspected dengue at the hospitals were confirmed dengue at the reference laboratory.

To accommodate difficult cases that have not been screened for dengue and typhoid fever, sites can include these cases in the retrospective component of the study. After discussion with the team on site and INA-RESPOND secretariat, and approval from the chair of INA-RESPOND, specimens can be stored at INA-RESPOND sites and sent to INA-RESPOND laboratory on a regular basis. However, since retrospective samples will not come with the detailed CRF data that the difficult case samples come with, they are less ideal. There are also fewer retrospective case spots in the study, and the selection process for those samples will naturally be much more stringent.

5. Specimen Collection and Testing

Specimens included in this protocol will vary depending on the source of the participants. For ongoing patients with difficult infections of unidentified etiology, all specimens will be collected and handled at each study site by laboratory personnel or designees. Appropriate precautions will be determined and followed by all personnel in drawing, handling, transporting, and storing of all biological specimens. Specimens will be labelled accurately and legibly with a unique identifier/code that does not contain any information capable of directly linking the specimens to the study participants. Specimens will be logged and tracked using an electronic specimen tracking/database system, and only authorized personnel will have access to the participant code and the samples.

For ongoing patients in outbreak situations, specimens will be received from designated Ministry of Health authorities **unless MoH authorities refer participants to the study team to be seen**. Specimen type determination and collection will occur independently of the study at the judgement of the health authorities **unless MoH authorities refer participants to the study team to be seen**. It is expected that participants will provide sample collection consent to health authorities but will not be asked to provide study consent **unless the participants are seen by the study team**. Therefore, these participants will be

enrolled in a de-identified manner, where coded samples without an identifying key are provided to the INA-RESPOND Reference Laboratory for analysis. Appropriate precautions will be followed in the handling, processing, and storage of all biological specimens, and the de-identified specimens will be logged and tracked using an electronic specimen tracking/database system.

For previously collected specimens to be included in the retrospective arm of the study, specimen type determination and collection have occurred independently of the study. Unless documented informed consent permitting sample use in future research is obtained, these participants will be enrolled in a de-identified manner, where coded samples without an identifying key are provided to the INA-RESPOND Reference Laboratory for analysis. Appropriate precautions will be followed in the handling, processing, and storage of all biological specimens, and the de-identified specimens will be logged and tracked using an electronic specimen tracking/database system.

Etiology identification for all participants will occur at the INA-RESPOND Reference Laboratory. Other relevant clinical laboratory testing requiring freshly drawn samples can be completed at the INA-RESPOND study sites. The laboratory testing to be completed at the INA-RESPOND Reference Laboratory will focus on the identification and/or confirmation of suspected etiologic agents in order to meet the objective of the study. Additional, relevant exploratory activities may include, but are not limited to, research tests to: a) study immune markers that might enable better management or prediction of outcomes for patients, b) study pathogenicity, and c) identify genetic markers that may increase or decrease disease susceptibility. Routine laboratory tests may also be completed as needed. Whenever possible, any specimen material remaining after study testing is complete will be cryopreserved and stored indefinitely for future research such as, but not limited to, developing and validating diagnostic tests, determining the evolution of pathogens, and determining host disease susceptibility.

The sharing of samples and/or data with entities outside of the study will follow regulations established in Material Transfer Agreements (MTAs).

If the initial testing fails to identify the suspected etiology, the study core team may develop and suggest a clinically-informed algorithm for further testing to be completed with the remaining specimens (Figure 5).

[figure not shown]

Figure 5 Flow of specimen testing at the INA-RESPOND Reference Laboratory

At the completion/termination of the study, specimens and data will either be destroyed or transferred to another existing protocol following approval from the INA-RESPOND Network Steering Committee and relevant IRBs. Any loss or unanticipated destruction of samples or data (i.e. due to freezer malfunction) that compromises the scientific integrity of the data collected for the study will be reported to the IRB.

The capacity of the INA RESPOND Reference Laboratory for pathogen identification will be described in Appendix 5.

6. Data management and Analysis

6.1. Data Management

For ongoing patients with difficult infections of unidentified etiology, participants will be coded with a unique identifier that does not contain any information capable of linking the data to the study participants. Only authorized personnel will have access to the participant code and the data. For ongoing patients in outbreak situations and retrospective patients, participants will also be coded with a unique identifier that does not contain any information capable of linking the data to the study participants. These participants will remain coded and de-

identified throughout the study since it is anticipated that study informed consent will not be obtained.

Data will be keyed and tracked using OpenClinica, RedCap, or other tools, as appropriate. Data will be periodically sent to the central data management center of INA-RESPOND and analyzed by the investigator team and approved partners. During the study and following study completion, data will be shared with the scientific community through peer-reviewed publications and presentations at local, national, and international meetings. IRB approval and approval from the INA-RESPOND Network Steering Committee must be sought prior to any sharing of data. Upon completion of the study, the final de-identified dataset will be made available to approved users under a specific data-sharing agreement as soon as possible, but no later than the acceptance for publication of the primary research manuscript. Any raw genome data and relevant associated metadata will be made available to the scientific community through submission to NCBI and appropriate databases such as GenBank. All study data will be shared in compliance with Indonesian legislation regarding the sharing of human participants data.

